1. What is your name?
 - a. First name
 - b. Middle name
 - c. Last name
2. How are you called in your home area?
3. What is the current physical location where you live?
 - a. District
 - b. City
 - c. Village
 - d. Estate
 - e. Plot number
 - f. Door number
 - g. Road name
4. Public Transportation to the house:
 - 4a. Type: F Bus F Boda boda F Matatu F Taxi F Other (specify)
 - 4b. Route number:
 - 4c. Stage Name
 - 4d. General Name of the Area
5. Walking directions to house from the stage?
6. Landmarks that aide in locating the household: (Names of schools, churches, businesses etc.)
7. Can you be reached by phone? Yes No
If yes,
 - 7 (i)What is the phone number 1?
 - 7 (ii)What is the phone number 2?
 - 7iii. Who carries the phone (tick one) self other, specify

B. SIGNIFICANT CONTACT

8. Is there another person who is ware of your HIV status that we can contact through phone if we are unable to reach you directly?
If no, skip to 9.
9. What is the name of this contact person?
a. First name
b. Middle name
c. Last name
10. What is the relationship of this person to you?
11. (a)What is the phone number 1?
(b) What is the phone number 2?

C. UPCOUNTRY INFORMATION

12. Do you have an upcountry home? Yes No
If no, skip to 19
13. What is the physical location of your upcountry home?
a. District
b. City
c. Village
d. Estate
e. Plot number
f. Door number
14. Specific directions to residence
15. Is there person located in your upcountry home whom we can contact if we are unable to reach you directly? Yes No
If no, skip to 19
16. What is the name of this contact person?
a. First name
b. Middle name
c. Last name
17. What is the relationship of this person to you?
18. Does this contact have a phone number? Yes No
If yes, specify: phone number 1, phone number 2

D. OTHER

Comment:

SHEDDING

Study ID Number ___ ___ ___

Interviewer Number ___ ___

Date of interview (day/month/year) ___ ___ / ___ ___ / ___ ___ ___ ___

Visit (tick one) Week 1 FU Week 2 FU Week 3 FU Other, specify _____

A: MEDICAL HISTORY

1. Has the patient experienced any lower abdominal pain since the last visit?

Yes No

If yes, indicate:

a. Duration ___ ___ days

b. Severity (scale from 1 to 5; 5 being most severe) ___ ___

2. Has the patient experienced any vaginal bleeding since the last visit?

Yes No

If yes, indicate:

a. Duration ___ ___ days

b. Volume

 Stain pants Requires sanitary pad Other, specify

3. Has the patient experienced any vaginal discharge since the last visit?

Yes No

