If yes, indicate:

c. Duration ___ ___ days

d. Color

 Yellow Brown White Clear

Other, specify

e. Smell

Malodorous

No odor

Other, specify

f. Volume

Stain pants

Requires sanitary pad

Other, specify

4. Has the patient experienced any fever after the last visit?

Yes No

If yes, specify duration ___ days

5. Did the patient seek medical care for these or other complaints?

Yes No

If yes, specify what complaint prompted the participant to seek care:

Abdominal pain

Fever

Vaginal Bleeding

Vaginal discharge

a. Other, specify

If yes, specify where the participant sought care:

Study clinic

Hope Center

Coptic Hospital

KNH

b. Other, specify

6. Was the participant's condition possibly due to a study procedure? (Ask if any of questions 1-4 is yes)

Yes No

If any question 1-4 is Yes and the condition is not expected as per study protocol, or is more severe than expected, fill an AE form.

7. Date of last menstrual cycle (dd/mm/yyyy)

8. Have you ever had vaginal sex since treatment? Yes No Refused

Other (specify) _____

8 (a). If yes, how many times? ___

8(b) If you have had vaginal sex since treatment, how often did you use condoms during sex?

Always (100%) Most of the time (75-99%)
 Half of the time (50%-74%) Sometimes (25-49%)
 Rarely (1-25%) Never (0%)
 Refused Don't know Other, specify _____

9. Do you think you may be currently pregnant? Yes No

10. Are you currently on antiretroviral medications?

Yes Refused Other, specify

No Don't know

If No, Refused, or Don't Know, skip to Q14

If yes, specify current medications and original start date.

- d4t, 3tc, nvp
- d4t, 3tc, efv
- azt, 3tc, nvp
- azt, 3tc, efv
- Other specify

Original ARV start date (dd/mm/yyyy)

11. During the last 7 days, how many antiretroviral pills did the patient MISS taking?

12. During the last 30 days, how many antiretroviral pills did the patient MISS taking?

(If Q11 and Q12 patient did not MISS taking any pills skip to Q14)

13. If the patient missed any doses, please specify reasons (check all that apply)

- Toxicity/ side effect
- Share with others
- Forgot
 - c. Felt better
- Too ill
- Stigma, disclosure or privacy issues
- Drug out of stock
- Patient lost or ran out of pills
- Delivery /travel problem
- Inability to pay
- Alcohol
- Depression
 - d. Other specify

B: DIAGNOSIS

14. Is there any new infection that was related to the procedure since the last visit?

Yes No

If yes, specify and fill an Adverse Event questionnaire:

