**** If Serious Adverse Event, contact a PI immediately after filling this form.****

PI Contacts: [name] – [contact], [name], [name] – [contact]

UANDIKISHAJI

Study ID Number _____ Hope ID Number _____ Interviewer Number _____

Date of interview (day/month/year) _____/_____/_____

Ulikubali kuhifadhi sampuli : Ndio La Sijui Nyingine, eleza

A: SOCIODEMOGRAPHICS

1. Tarehe ya kuzaliwa (siku/mwezi/mwaka) _____/_____/_____

2. Miaka _____ years

3. Ulikamilisha miaka ngapi ya elimu? _____ years

4. Elimu ya juu zaidi uliyokamilisha? Hakuna
Msingi

Sekondari

Elimu ya juu/ Chuo Kikuu

Sijui

Amekataa

Nyingine, eleza

5. Hali ya ndoa (jibu moja) Ndoa (mke mmoja)

Ndoa (wake wengi)

Pekee

Talaka/Tenganishwa

Mjane

Amekataa

Kuishi pamoja

Nyingine eleza

6. Ajira (jibu moga): Kazi inayokupa mshahara

Kujiajiri

- Mama wa nyumbani
- Hujaajiriwa
- Mfanyikazi wa kawaida
- Amekataa
- Nyingine, eleza
7. Kipato cha kaya kwa mwezi (jibu moja): Hakuna
- < 5000 Ksh
- 5001 – 10000 Ksh
- 10001 – 15,000 Ksh
- >15,000 Ksh
- Sijui
- Amekataa

B: HISTORIA YA KUFANYA MAPENZI

8. Ulikuwa na miaka mingapi ulipofanya ngono ya uke mara ya kwanza? ___
Sijui Amekataa Hujawahi Nyingine, eleza
9. Umewahi kuwa na wapenzi wangapi wa ngono? ___
Sijui Amekataa
Nyingine, eleza _____
10. Umekuwa na wapenzi wangapi tofauti wa ngono mwaka wa mwisho? ___
___ Sijui Amekataa Nyingine, eleza
11. Umefanya ngono katika mwezi wa mwisho? (If no, don't know, refused, skip to 14) Ndio La Sijui Amekataa Nyingine, eleza
12. Ni mara ngapi umetumia mpira wakati wa ngono katika mwezi uliopita?
Kila wakati (100%) Wengi wa wakati huo (75-99%)
Nusu ya mudu (50%-74%) Wakati mwingine (25-49%)
Mara chache (1-25%) Kamwe (0%)
Amekataa Sijui
Nyingine, eleza
13. Je, unafikiri unaweza kuwa ma mimba sasa? Ndio La Sijui
Amekataa Nyingine, eleza

C: SARATANI YA UZAZI HISTORIA YA UCHUNGUZI

14. Hapo awali, umewahi kupimwa saratani ya uzazi? Ndio La
Sijui Alikataa Nyingine, eleza

If no, don't know or refused skip to 20.

15. Uchunguzi gani wa saratani ya uzazi uliofanyiwa hivi karibuni? (jibu moja)

- Pap smear
- Ukaguzi na asetiki aside
- HPV
- Nyingine, eleza : _____
- Sijui
- Amekataa

16. Uchunguzi huu wa hivi karibuni ulifanyiwa wapi?

- Coptic
- KNH
- Amekataa Sijui
- Nyingine, eleza

17. Uchunguzi huu ulifanyiwa wapi?

sijui

18. Majibu yalikuwa nini?

- Kawaida
- Usiokuwa ya kawaida, eleza _____
- Sijui
- Amekataa

19. Ulipokea matibabu yoyote ya kizazi au upasuaji kwasababu ya majibu ya hii uchunguzi?

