b. Jina la katikati
c. Jina la mwisho
35. Uhusiano gani upo kati yako na mtu huyu ?
36. Je huyu mtu ako na simu? Ndiyo La
Iwapo ndiyo , fafanua

(a) Nambari yake ya simu1?
(b) Nambari yake ya simu2?

D. ANDRA

Maoni

SHEDDING

Study ID Number ___ ___ ___

Interviewer Number ___ ___

Date of interview (day/month/year) ___ ___ / ___ ___ / ___ ___ ___ ___

Visit (tick one) Week 1 FU Week 2 FU Week 3 FU Other, specify _____

A: MEDICAL HISTORY

1. Unasikia maumivu ya tumbo ya chini?

ndio la

(Ndio, fafanua)

- a. muda wa ___ ___ (siku)
- b. Ukali (kidogo 1-5, 5 kuwakali zaidi)

9. Umekuwa na historia ya kutokwa na damu ambaye si yakawaida? Fafanua

Ndio La

(Ndio, fafanua)

- g. muda wa ___ ___ siku
- h. kiasi
- doasuruali)

Inahitajipediya usafi

Mwingine, eleza

Unatokwa na majimaji ya uke yasiyo ya kawaida?

10.

Ndio la

(Ndio, fafanua)

- i. muda wa ___ siku)
- j. rangi ya
 - Majano

hudurungi

nyeupe

wazi

Nyingine ,fafanua

k. harufu

Harufu mbaya

Hakunaharufu

Mengine,eleza

l. kiasi

inadoasuruali

Inahitajipediya usafi

Mengine,eleza

11. Mgonjwa amekuwa nahoma yoyotebaada ya ziara yamwisho?

Ndio la

kama ndio, fafaua muda...siku

12. Je,mgonjwaametafutahuduma zamatibabu kwa ajili yahaya aumalalamiko mengine?

Ndio La

If yes, specify what complaint prompted the participant to seek care:

Uchungu wa tumbo ya chini

Homa

Damu kutoka uzazi wa kike

Uchafu unaotoka katika uzazi wa kike

e. Mengine, fafaua

If yes, specify where the participant sought care:

Study clinic

Hope Center

Coptic Hospital

KNH

f. Other, specify

13. Was the participant's condition possibly due to a study procedure? (Ask if any of questions 1-4 is yes)

Yes No

If yes, fill out a Complications questionnaire.

14. Damu yako ya mwezi ya mwisho ilikuwa lini? (dd/mm/yyyy)

15. Umewahi fanya ngono uke tangu utibiwe? Ndio la Kataa

Nyingine fafaua _____

8 (a). Ndio, mara ngapi? __

8(b) Kamawamefanya mapenziuketangumatibabu,je,ni mara ngapikutumia kondomu wakati wa ngono?

Kila wakati (100%) Wengi wa wakati huo (75-99%)
 Nusu ya mudu (50%-74%) Wakati mwingine (25-49%)
 Mara chache (1-25%) Kamwe (0%)
 Amekataa Sijui
 Nyingine, eleza

9. Unafikiri unaweza kuwa mjamzito

Ndio la

10. Kwa sasa unatumia madawa ya kupungua makali ya virusi

Ndio Kataa Nyingine,fafaua

La Sijui

Ndio, fafaua madawa unayo tumia sasa na tarehe uliyo yaanza

- d4t, 3tc, nvp
- d4t, 3tc, efv
- azt, 3tc, nvp
- azt, 3tc, efv
- zingine, fafanua

Tarehe ya kuanza ARV awali (dd /mm /yyyy)

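### Three of the four symptom items on the Kiswahili Shedding form differ from the English form in recall window or threshold, so post-treatment symptoms are not comparable across interview languages

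*Combined protocol and SAP*

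**What the plan says.** **English Shedding form, Section A.** The first three symptom items are anchored to the previous visit and cover any occurrence: "Has the patient experienced any lower abdominal pain since the last visit", "Has the patient experienced any vaginal bleeding since the last visit" and "Has the patient experienced any vaginal discharge since the last visit". The fever item uses the same window.

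**Kiswahili Shedding form, Section A.** The pain item reads "Unasikia maumivu ya tumbo ya chini", a present-tense question about feeling lower abdominal pain. The bleeding item reads "Umekuwa na historia ya kutokwa na damu ambaye si yakawaida", which asks about a history of bleeding that is not normal and sets no period. The discharge item asks whether she is passing vaginal fluid that is not normal, again in the present tense. The fever item asks about any fever after the last visit, as in English.

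**What follows a positive answer.** Both versions ask whether the condition may be due to a study procedure only if one of the four symptom items is positive. The English form then says that if "the condition is not expected as per study protocol, or is more severe than expected, fill an AE form". The Kiswahili form says "If yes, fill out a Complications questionnaire". In Section B, Kiswahili items 14 and 15 (new infection, new complication) name a Complications and/or an Adverse Event questionnaire. The English items name only the latter.

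**Enrollment form, Q17.** The English item asks when the last screening test was done. The Kiswahili item reads "Uchunguzi huu ulifanyiwa wapi", which asks where and so repeats Q16.

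**The concern.** The protocol section headed Adverse Events (AEs) treats abdominal pain beyond 2-3 days, and vaginal bleeding or discharge without any restriction to abnormal, as events to be assessed at visits. The Shedding form is the scripted instrument for this in the three weeks after treatment. If its wording depends on language, the recorded frequency and duration of symptoms depend partly on which version was read out.

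These data have a use. The section on quality control of study procedures has the rate and type of complications reviewed bi-monthly, and the section on reporting adverse events sends serious and non-serious events to the DSMB. The protocol describes a staff check of the Kiswahili translation for the consent documents. It describes none for the data collection forms.

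**Working it through.** No stated figure is at stake, so the check is a comparison of the two versions.

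**1. Items side by side**

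| Symptom | English | Kiswahili | Likely effect |
|---|---|---|---|
| Pain | any, since previous visit | present tense | narrower; resolved pain is lost |
| Bleeding | any, since previous visit | not normal, no time limit | narrower in threshold, wider in time; direction unknown |
| Discharge | any, since previous visit | present tense, not normal | narrower on both counts |
| Fever | any, since previous visit | same | none |

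Three of four items lose the window, and two of four gain a threshold.

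**2. Is this only a nuance of translation?** The documents suggest not. The three Kiswahili items closely resemble baseline questions on the Randomization form, where the English counterparts ask about current lower abdominal pain, abnormal discharge and a history of abnormal bleeding. The post-treatment form thus asks near-baseline questions. The fever item shows that the window could be expressed.

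**3. A worked case.** Shedding visits are weekly. Suppose a woman has pain for four days after treatment and none at the week 1 visit. Four days exceeds 2-3 days, so the pain falls under the protocol's AE description. In English she answers yes and gives a duration of four days. In Kiswahili the correct answer to the pain item is no. If the other three items are also negative, the attribution item is not asked. Section B does not recover the case: item 14 concerns infection, and item 15 concerns complications diagnosed that day.

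**4. The form named.** The list of 16 questionnaires under Databases contains no Complications form, and none appears among the forms in the available text. The quality control section says complication data are collected on the Adverse Event form, and that form is printed, with boxes for the three shedding visits. The simplest reading is that the Kiswahili version was not updated.

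**5. The triggers.** The English trigger leaves out symptoms that are expected and of expected severity. The Kiswahili trigger takes any condition possibly due to a procedure. The AE section has every untoward occurrence recorded, related or not. Neither trigger matches that definition, and on expectedness the English one is the narrower.

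**6. Size, as an illustration only.** Let s be the share of women interviewed in Kiswahili and e the sensitivity of a narrowed Kiswahili item relative to the English one. Neither is in the documents. Then recorded/true = 1 − s(1 − e). Assume s from 0.25 to 1 and e from 0.5 to 0.9:

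- s = 0.25, e = 0.9: 1 − 0.25 × 0.1 = 0.975
- s = 1, e = 0.5: 1 − 1 × 0.5 = 0.50

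The recorded frequency would lie anywhere from 50% to 97.5% of the true one. To see the effect on a comparison, take the 8% (LEEP) and 2% (cryotherapy) complication rates from the comparative study in the Background. Equal loss in both arms leaves the risk ratio at 8/2 = 4.0. The 6-point difference becomes 6 × 0.975 = 5.85 to 6 × 0.50 = 3.0 points. These are consequences of assumed inputs, not estimates for this trial.

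**The case against.** The stronger reading is that harms are under-recorded in women interviewed in Kiswahili. A reader might infer this, but the documents do not show it:

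- **Bleeding.** The item has no time limit. Bleeding that has stopped is not excluded by tense, and bleeding from before treatment could be counted.
- **Discharge.** The risk statement in the Ethics section expects it to last about two weeks. It would usually still be present at week 1, so the restriction to abnormal matters more there than the tense. That statement also does not show what women themselves were told to regard as normal.
- **Other routes.** The protocol has staff ask about new or worsening problems and record any adverse event at the time or at the next visit. The Kiswahili care-seeking item corresponds to the English one.

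A reader might also infer that adverse event forms go unfilled because the Complications form is not in use. That goes too far. Kiswahili items 14 and 15 name the Adverse Event form, and the Kiswahili attribution trigger could prompt more forms rather than fewer. Absence from the list of 16 proves little, since the Adverse Event form is not listed there either, and some form pages are not in the available text.

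Nor is a point figure supportable. Guessing that half the interviews are in Kiswahili and half of short-lived symptoms are missed gives 0.5 × 0.5 = 25%, but neither input is in the documents.

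Two further points stand. Under Entry, the Shedding form is not among those completed on paper, and the wording of the electronic version is not shown. Statistical Methods specifies no analysis of these items, and the safety stopping criterion concerns serious adverse effects.

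None of this removes the difference in wording. The general inquiry is a real second route, but the printed Shedding form has no scripted item for it. The broader Kiswahili trigger cannot act on a symptom already answered no.

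**Conclusion.** The point holds as a matter of comparability. Pain, bleeding and discharge are not the same questions in the two languages, so symptom frequencies and durations pooled across languages mix different definitions. Under-recording is plausible for pain and discharge, and the direction for bleeding is unknown. This rests on reading the printed Kiswahili form as the wording used in interviews; the electronic version may differ.

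The size cannot be estimated without the language mix. No shift towards either arm is expected, because interview language is not determined by the allocated treatment. The main consequence is for absolute complication rates and the reviews that use them, and the primary recurrence comparison is untouched. The attribution item's reference to an unlisted form is an inconsistency to resolve, not evidence that events were lost. The Enrollment Q17 slip is separate and minor: it concerns the date of a past screening test, which no stated analysis uses.

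**What to change.** 1. Re-translate the Kiswahili pain, bleeding and discharge items so that each asks about any occurrence since the previous visit. Back-translate them, and make the same change in any electronic version.
2. Replace the Complications questionnaire with the Adverse Event form in the Kiswahili attribution item and in Section B items 14 and 15.
3. Reconcile the completion triggers of the two versions with the protocol's AE definition. Do not simply copy the English trigger, which is the narrower one on expectedness.
4. Record interview language, for which neither version has a field, and report symptom frequencies by language.
5. Correct Kiswahili Enrollment Q17 to ask when. The Kiswahili Randomization form already uses the word lini for this.
6. Withdraw the superseded Kiswahili version.

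The cost is re-translation of a few lines and re-approval of two forms, Shedding (both languages if the trigger wording changes) and Enrollment. No visit or procedure is added. Data already collected in Kiswahili would need to be identified and described separately.

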- Embakasi Other (specify)

4b. If western or Nyanza, specify area: (tick one)

- Kisumu Rural Maseno
- Siaya Chulaimbo
- Vihiga Lela
- Kakamega Other (Specify)
- Luanda

5. Email

6. Physical Address

HOPE CLINIC ADDRESS AND INTAKE

7. How long has the client stayed at this residence?

- Less than a year Greater than a year

8. How long does the client plan to stay at this residence?

- Less than a year Greater than a year

9. Phone number (Cell)

9a. Relationship to phone owner (tick one)

- Self Employer

- Relative Other (specify)

- Friend

10. Phone number (Landline)

10a. Relationship to phone owner (tick one)

- Self Employer

- Relative Other (specify)

- Friend

Emergency contact (in case we cannot reach the patient)

11. Name (Last, First, Middle)

11a. Relationship to client (tick one)

- Self Employer

- Relative Other (specify)

- Friend

- Husband/Wife

11b. Phone No.

Clients transferring from Pediatric Clinic

12. Pediatric Hopeid

For the data use only (tick after scanning the form)

Scanned Date ___ / ___ / _____ Name of data person

HOPE CLINIC COUNSELING ADHERENCE #1

HOPE ID Number

Site Code

Today's date (DD.MM.YYYY)

 /
 /

Interviewer number

Checklist	Tick
Explain about HIV and how it affects the body	
Explain about CD4 cells and why it is necessary to measure the CD4 count	
Explain the difference between HIV and AIDS.	
Explain about ARV.	
Explain ARV is not a cure.	
Explain the cause of resistance.	
Explain treatment failure	
Explain importance of adherence.	
Explain problem of side effects.	
Have patient think about life long commitment of therapy.	
Have patient think about ability to follow up care	
Explore patient support system	
Discuss adherence promotion strategies e.g. treatment buddy, pill diary e.t.c	

2. Identify barriers to adherence (tick all that apply)

- | | |
|---|--|
|  Poor Communication |  Lack of social support |
|  Inadequate understanding about HIV/AIDS |  Alcohol/ Drug use |
|  Failure to disclose status |  None |
|  Mental State |  Others (specify) |
|  Stigma | 

 |
|  Low literacy | |

3. Does the patient need to move forward with the protocol or to repeat counselling adherence #1 ?

- Move forward Repeat Counselling Adherence # 1

Notes/Remarks

For the data use only (tick after scanning the form)

Scanned Date ___ / ___ / _____ Name of data person

HOPE CLINIC COUNSELING ADHERENCE #2

HOPE ID Number

Site Code

Today's date (DD.MM.YYYY)

Interviewer number

--	--	--	--

--

--

--	--	--	--	--

--	--	--

Score scale: 1-Poor 2-Fair 3-Good

Section A: Knowledge Assessment

Question	Rationale	Score
1. What do you know about ARVs?	Assess whether information given in Counseling Adherence#1 has been understood.	
2. What are the names of any ARVs?	Assess the client knows that AZT, NVP, etc. are ARVs, but septrin is not	
3. How do ARVs work?	Assess the client's knowledge of basic ARV action (especially that ARV is not a cure for HIV infection.)	
4. What side effects are associated with ARVs? What do you know about them?	Assess client's knowledge of side effects related to his/her ARV regimen and the appropriate response to deal with side effects.	
5. How long should you normally take ARVs?	Assess whether client knows ARV is life long treatment.	
6. What happens if you dont take ARVs consistently?	Assess whether client understands the problem of resistance given ARV interruptions.	
7. What is the purpose of CD4 counts?	Assess whether client knows that CD4 count is a laboratory indicator for monitoring the effect of ARV	
8. What are your expectations from ARVs?	Assess whether client has realistic expectations, e.g., prolonging life, keeping them well enough from their family, e.t.c. Assess for false expectations, e.g., a cure for HIV, e.t.c	
9. Can someone still transmit HIV while taking ARVs?	Assess/review need for continued prevention e.g. condom use.	
If total score is less than 18, patient has failed section A If total score is 18 or above, the patient passes section A		Total Score:  

Section B: Counselor Assessment

Question	Rationale	Score
10. Assess for barriers that help determine capability for followup	Assess whether client can attend HIV clinic for follow up medical and counselling care	
11. Ask the client whether s/he has a relative/friend whom s/he can rely on to support her/him taking ARV	Assess availability of support from home	
12. On a scale of 1 to 5 (5 being most ready, 1 being least), please rate the client's ability to adhere to medications	Score 1: Patient will adhere to the ARVs very poorly (Misses more than half the doses) Score 2: Patient will likely miss doses of ARVs on a regular basis (misses up to 50% of doses) Score 3: Patient will only miss some doses of ARVs (1 dose a month at most) Score 4: Patient will rarely miss a dose of ARVs (1 dose every 6 months at most) Score 5: Patient will almost never miss any doses (1 dose every year at most)	
If total score is 2 or below on question 12, patient fails section B If total score is 3 or above question 12, patient passes section B		

HOPE CLINIC COUNSELING ADHERENCE #2

Section C: Participant Assessment

Question	Rationale	Score
13. Ask the client if s/he can come to HIV clinic for regular follow-up?	YES or NO answer	 Yes  No
14. Do you want to start ARV treatment now?	YES or NO answer	 Yes  No
If any answers in this section are "NO" then patient fails Section C		

Section D: Final Assessment

15. a) Did the patient pass section A, B and C?

Yes (Patient moves forward) No

b) If NO, is the patient scheduled to repeat counseling?

Yes No

Notes/Remarks

For the data use only (tick after scanning the form)

Scanned Date ___/___/_____ Name of data person

HOPE CLINIC COUNSELING ADHERENCE #3

To be performed 1 month after starting ARVs

HOPE ID Number

Site Code

Today's date (DD.MM.YYYY)

Interviewer number

Score scale: 1- poor 2-Fair 3-Good

Section A: Knowledge Assessment

Question	Rationale	Score
1. What do you know about ARVs?	Assess whether information given in Counseling Adherence#1 has been understood.	
2. What are the names of your medications and dosage?	Assess whether the client knows his/her medication and dosage.	
3. How do ARVs work?	Assess the client's knowledge of basic ARV action (especially that ARV is not a cure for HIV infection.)	
4. What side effects are associated with ARVs and what do you do if you have side effects?	Assess client's knowledge of side effects related to his/her ARV regimen and the appropriate response to deal with side effects.	
5. How long should you normally take ARVs?	Assess whether client knows ARV is life long treatment.	
6. What happens if you don't take your ARVs consistently?	Assess whether client understands the problem of resistance given ARV interruptions.	
7. What is the purpose of CD4 counts?	Assess whether client knows that CD4 count is a laboratory indicator for monitoring the effect of ARV	
8. What are your expectations from ARVs?	Assess whether client has realistic expectations, e.g. prolonged life, keeping them well enough from thier family, etc. Assess for false expectations, e.g., a cure for HIV, etc.	
9. How can someone still transmit HIV while taking ARVs?	Assess review need for continued prevention e.g. condom use	
Total Score		

Section B: Counselor Assessment

Question	Rationale	Score
10. During the last 7 days how many pills did the patient MISS taking?	Get exact number of pills missed	
11. On a scale of 1 to 5 (5 being most ready, 1 being least), please rate the client's ability to adhere to medications?	Score 1: Patient will adhere to the ARVs very poorly (Misses more than half the doses) Score 2: Patient will likely miss doses of ARVs ona regular basis (Misses up to 50% of doses) Score 3: Patient will only miss some doses of ARVs (1 dose a month at most) Score 4: Patient will rarely miss a dose of ARV (1 dose every 6 months at most) Score 5: Patient will almost never miss any doses (1 dose every year at most)	

Notes/Remarks

For the data use only (tick after scanning the form)

Scanned Date ___/___/_____ Name of data person

HOPE CLINIC PHONE NUMBER AND ADDRESS UPDATE FORM

HOPE ID Number

Site Code	Today's Date (DD.MM.YYYY)	Interviewer number
    	 /  /    	  

Name (First, Middle,last)

1. Has the client's phone number changed? Yes No *(If Yes go to 2, If No go to 4)*

2. Phone number (Cell)

2a. Relationship to phone owner (tick one)

- | | |
|--|---|
|  Self |  Friend |
|  Husband or wife |  Employer |
|  Relative |  Other (specify)  |

3. Phone number (Landline)

3a. Relationship to phone owner (tick one)

- | | |
|--|---|
|  Self |  Friend |
|  Husband or wife |  Employer |
|  Relative |  Other (specify)  |

4. Has the client moved? Yes No *(If Yes go to 5, If No go to 7)*

5. Physical Address

6. In which region does the client now reside (stay) *(For Maseno, check 2nd, 3rd and where applicable 4th column)*

- | | | |
|--|---|---|
|  Nairobi province (See 6a) |  Central province |  Eastern province |
|  Nyanza province (See 6b) |  Rift Valley province |  Coast province |
|  Western province (See 6b) |  North Eastern province | |

6a. If Nairobi province, specify area: (tick one)

- | | |
|---|--|
|  Langata/Kibera |  Westlands |
|  Starehe |  Kasarani |
|  Dagoretti |  Kamukunji |
|  Makadara |  Eastlands/Industrial Area |
|  Embakasi |  Other(Specify)  |

6b. If western or Nyanza, specify area: (tick one)

- | | |
|---------------------------------------|--|
|  Kisumu Rural |  Maseno |
|  Siaya |  Chulaimbo |
|  Vihiga |  Lela |
|  Kakamega |  Other(specify)  |
|  Luanda | |

HOPE CLINIC

PHONE NUMBER AND ADDRESS UPDATE FORM

7. Has the client's email changed? Yes No *(If Yes go to 8, If No go to 9)*

8. Email

Emergency contact (in case we cannot reach the patient)

9. Has the client's emergency contact changed? Yes No *(If Yes go to 10)*

10. Name (Last, First, Middle)

10a. Relationship to client (tick one)

Self Employer

Relative Other (specify)

Friend

Husband/Wife

10b. Phone No.

For the data use only (tick after scanning the form)

Scanned Date ___/___/_____ Name of data person

HOPE CLINIC PATIENT PHONE CONTACT FORM

HOPE ID Number

Site Code **Today's Date (DD.MM.YYYY)** **Interviewer number**
 / /

1. Date of phone contact (DD/MM/YYYY) / /
2. Did you talk to the patient or patient's contact?
 - Yes, talked to patient *(Go to 4)*
 - Yes, talked to patient's contact *(Go to 3)*
 - No *(Go to 4)*
3. If talked to patient's contact, who was the source of information *(tick one)*
 - Clinician/clinic staff Employer Caregiver
 - Spouse or partner Friend Treatment supporter
 - Family member/Relative Neighbour Other (specify)
 - Mother/Father
- 3a. Did the source of information have credible knowledge for whether the patient was alive or dead?
 - Yes, credible and patient confirmed alive *(Go to 4)*
 - Yes, credible and patient confirmed dead *(Go to 9 and complete Mortality form)*
 - Source did not know whether patient was dead or alive *(Go to 4)*
4. What was the reason for calling or contacting the patient or patient's contact?
 - Patient missed clinic appointment *(Go to 5)*
 - Patient missed pharmacy pickup *(Go to 6)*
 - Other (specify) *(Go to 7)*
5. Reasons for missed clinic appointment *(tick all that apply)*
 - N/A, did not reach patient or patient's contact Unable to attend because of health problems
 - No longer willing to attend Family problems
 - Wait time too long Client will go to faith healer
 - Conflict with work Unwilling to disclose
 - Financial problems Other (specify)
 - Client moved or relocated
6. Reasons for missed pharmacy pick up *(tick all that apply)*
 - Unable to attend because of health problems Got medication somewhere else
 - Family problems Client will go to faith healer
 - Conflict with work Unwilling to disclose
 - Financial problems N/A, did not reach patient
 - Client moved or relocated Other (specify)

7. If talked to patient, did the patient wish to remain in the clinic?

- Yes (Go to 7a)
- No (Go to 8 and complete Exit form)
- N/A, did not talk to patient (Go to 9)

7a. Did the patient schedule a clinic appointment? Yes No (If YES go to 7b, If NO go to 7d)

7b. If YES, date of scheduled appointment (DD/MM/YYYY) / /

7d. If NO, why did the patient not schedule an appointment (tick all that apply)

- Unable to attend because of health problems
- Family problems
- Conflict with work
- Financial problems
- Client moved or relocated
- Client lives too far away
- Other (specify)

8. If the patient does not wish to return to the clinic, specify why (tick all that apply)

- Not willing to attend
- Attend clinic closer to home
- Wait time too long
- Conflict with work
- Financial problems
- Unwilling to attend because of health problems
- Family problems
- Client will go to faith healer
- Not willing to disclose HIV status
- Referred elsewhere
- Unknown
- Other (specify)

9. Did you refer the client to any of the following (tick all that apply)

- Clinic
- Counselor
- Nutritionist
- HBC
- None

Comments

For the data use only (tick after scanning the form)

Scanned Date ___/___/_____ Name of data person

HOPE CLINIC

Counseling General Session

HOPE ID Number

Site Code

Today's Date (DD/MM/YYYY)

Interviewer number

Notes

What was the focus of the session? (tick all that apply)

- Pretest
- Hygiene
- Family planning
- Crisis
- Discordance
- Sex and sexuality

- Post-test
- PMTCT
- Child(ren)
- Opportunistic infection
- Welfare
- Drug therapy

- HIV/STD Prevention
- Nutrition
- Bereavement
- Spirituality
- Disclosure
- Child transfer to Adult Clinic
- Other (specify)

For the data use only (tick after scanning the form)

Scanned Date ___ / ___ / _____ Name of data person

HOPE CLINIC

COUNSELOR SCREENING

HOPE ID Number

Site Code

Today's date (DD.MM.YYYY)

Interviewer number

1. How many children do you have or care for? If = 0 go to 2

1a. Describe HIV test results and HIV care for each child.

	Test Result	Receiving HIV care?	Receiving HAART?	Receiving HAART and/or HIV care at Hope Clinic?
1	 Positive  Negative  Unknown  Not tested	 Yes  Unknown  No  N/A	 Yes  Unknown  No  N/A	 Yes  Unknown  No  N/A
2	 Positive  Negative  Unknown  Not tested	 Yes  Unknown  No  N/A	 Yes  Unknown  No  N/A	 Yes  Unknown  No  N/A
3	 Positive  Negative  Unknown  Not tested	 Yes  Unknown  No  N/A	 Yes  Unknown  No  N/A	 Yes  Unknown  No  N/A
4	 Positive  Negative  Unknown  not tested	 Yes  Unknown  No  N/A	 Yes  Unknown  No  N/A	 Yes  Unknown  No  N/A

2. Have you revealed your serostatus to:

- a. Spouse(s) or steady partner(s) All Some None Has no spouse
- b. Casual or non-casual partner(s) All Some None Has no partner
- c. Parents All Some None Has no parents
- d. Siblings All Some None Has no siblings
- e. Children All Some None Has no children
- f. Friends All Some None Has no friends
- g. Others All Some No one else Specify

3. Who forms your closest social support (tick one)

- Spouse/steady partner Sibling
- Mother Other (specify)
- Father No social supporter
- Friend

3a. Have you informed this person of your serostatus?

- Yes No N/A

4. Have you ever had sex? Yes No (If YES, go to 5, If NO go to 13)

5. How many spouse(s) or steady partner(s) do you have? (If = 0 go to 6)

5a. Describe HIV test results and HIV care for each spouse(s) or steady partner(s)

	Relationship	Test Result	Receiving HIV care?	Receiving HAART?	Receiving HAART and/or HIV care at Hope Clinic?
1	 Spouse  Steady partner	 Positive  Negative  Unknown  not tested	 Yes  No  Unknown  N/A	 Yes  No  Unknown  N/A	 Yes  No  Unknown  N/A
2	 Spouse  Steady partner	 Positive  Negative  Unknown  Not tested	 Yes  No  Unknown  N/A	 Yes  No  Unknown  N/A	 Yes  No  Unknown  N/A
3	 Spouse  Steady partner	 Positive  Negative  Unknown  Not tested	 Yes  No  Unknown  N/A	 Yes  No  Unknown  N/A	 Yes  No  Unknown  N/A
4	 Spouse  Steady partner	 Positive  Negative  Unknown  not tested	 Yes  No  Unknown  N/A	 Yes  No  Unknown  N/A	 Yes  No  Unknown  N/A
5	 Spouse  Steady partner	 Positive  Negative  Unknown  Not tested	 Yes  No  Unknown  N/A	 Yes  No  Unknown  N/A	 Yes  No  Unknown  N/A
6	 Spouse  Steady partner	 Positive  Negative  Unknown  Not tested	 Yes  No  Unknown  N/A	 Yes  No  Unknown  N/A	 Yes  No  Unknown  N/A

6. How many different casual or non-steady partner(s) did you have in the past year?
7. In the past year, how many different sexual partners have you had, including your spouse(s) and steady partner(s)?
8. During your lifetime have you had sex with
 Men Only Women Only Both None Refused to answer
9. Describe your condom use in the past 12 months todate:-
 a.Spouse(s) or steady partiners *(Tick one)*
 Never Sometimes Always No sex in past 12 months No spouse/steady partner
 b.Non- steady partiners. *(Tick one)*
 Never Sometimes Always No sex in past 12 months No Non-steady partner
10. Did you use a condom during your last sexual encounter
 No Yes Refused to answer
11. Are you able to talk about using condoms with your spouse(s) or steady partner(s)?
 No Yes Refused to answer No spouse/steady partner Dont know
- 11a. Are you able to say NO to sex if your spouse or steady partner will not use a condom?
 No Yes No spouse/steady partner Refused to answer Don't know
12. Are you able to talk about condoms with your casual or non-steady partner(s)?
 Yes No No non-steady partner(s) Refused to answer Don't know
- 12a. Are you able to say NO to sex if your casual or non-steady partner(s) will not use a condom?
 No Yes No non-steady partner(s) Refused to answer Don't know
13. Are you Circumcised ?*(Ask Male client only)*
 Yes No Refused to answer Female client
14. Do you feel neglected by anyone *(tick all that apply)*
 Family Friends Health care workers None Others (specify)
15. Counselor, does the client need a treatment supporter? Yes No *(If yes go to 15a, if no go 16)*
- 15a. If YES why? specify (Tick all that apply)
 Client requests treatment supporter
 Physically disabled
 Mentally disabled
 Other (specify)

16. Counselor is this client recommended for homecare? Yes No

16a. If YES, specify why? (Tick all that apply)

- Physically or mentally disabled adult
- Adult dependent on care-giver
- Client requests a home visit
- Disclosure (patient would like help disclosing status to family members)
- Family testing (client would like other family members to be tested)
- Other (specify)

17. Have you explained/discussed or checked the following with the Client?

Checklist	Tick (if Yes)	Tick (if No)
1. Overview of HOPE Center Program and Services		
2. Importance of commitment to the program		
3. Policy for adherence and clinic attendance		
4. Patients enrollment status in other programs or facilities		
5. Patients long term goals for health management at our program		

Notes / Assessment

For the data use only (tick after scanning the form)

Scanned Date ___ / ___ / _____ Name of data person

HOPE CLINIC ADULT LOCATOR FORM

HOPE ID Number

Site Code

Today's Date (DD/MM/YYYY)

//

Interviewer number

1. Name (Last, First, Middle)

2. Gender Male Female

3. Age (Years)

CLIENT'S RESIDENTIAL AND TELEPHONE CONTACT INFORMATION

4. Public Transportation to the house:

4a. Type

Bus Citi Hoppa Matatu Taxi Other(specify)

4b. Number

4c. Stage Name

4d. General name of the area

5. Walking directions to house from the stage?

6. Landmarks that aide in locating the household: (Schools, churches, businesses etc.)

7. How is the Client or Caregiver called or referred to in home area:

8. Primary Telephone Contact:

Mobile Landline Unknown

8a. Line belongs to:

- | | |
|---|---|
|  Client |  Friend |
|  Parent |  Neighbour |
|  Caregiver |  Nerby Simu ya Jamii |
